## Study Procedures

**If you uploaded a separate research protocol document in the 'Research Protocol' page, cite the applicable section and page numbers from that document in the answer boxes below. (If this study is a collaborative UM/VA study please list each procedure that is being conducted and the locations where it is being conducted.)**

1 \* Describe all procedures being performed for research purposes only (these procedures would not be done if individuals were not in the study) and when they are performed, including procedures being performed to monitor subjects for safety or to minimize risks:

This is a pilot randomized controlled trial that works within the framework of the Obesity-Related Behavioral Intervention Trials (ORBIT) model for behavioral treatment development. This trial will assess the feasibility of our methods to conduct a 12-week randomized controlled trial that implements TRE as well as the preliminary efficacy of TRE vs. a control group on cancer-related fatigue. We will recruit 50 patients who are 2 months-2 years post-treatment for cancer (e.g., surgery, radiation, chemotherapy) and are suffering from moderate-severe cancer-related fatigue. They will be randomized 1:1 intervention:control (approximately 15 in each arm). This will be an open label study because, due to the nature of the intervention, it is not possible to blind participants and, due to the active involvement of the PI in data acquisition, it is not feasible to blind the PI. Participants will be told that we are using a new smartphone app that helps us explore how behaviors such as diet, exercise, and sleep are related to fatigue; some people will be asked to also engage in TRE while some will be asked to follow their normal eating patterns.

Participants will be recruited from the University of Maryland Medical System, including the Greenebaum Comprehensive Cancer Center, St. Joseph Medical Center, Upper Chesapeake Medical Center, and Baltimore Washington Medical Center. The whole study can be conducted remotely, but if the participant would prefer an in-person visit for consenting or any other study activity, we will meet them at either Greenebaum Cancer Center or the School of Nursing.

Potential participants will be identified using four methods: (i) screening medical records, (ii) direct referral from providers (e.g., nurses, nurse navigators, physicians), (iii) flyers, and (iv) advertising via standard UMB- and ICTR-networks. The study staff will screen for potential participants using EPIC or, alternatively, patients may be referred to the study team by a provider or acquaintance. Initial contact will occur via the following methods: i) the treating oncologist or a member of the medical team (e.g., nurse practitioner) will introduce the study to the participant via a clinic appointment (in person or telehealth) and inquire if it would be okay for our study team to talk with them after their visit or contact them, ii) with approval of the treating oncologist or a designee, a recruitment letter will be sent to the potential participant briefly describing the study and asking them to contact us if they would like more information, and iii) with approval of the treating oncologist or a designee, a message will be sent to the potential participant via MyPortfolio briefly describing the study and asking them to contact us if they would like more information. If a potential participant is interested, the study team will provide more information about the study in-person or via phone.

The study activities are briefly described here; the study schema is illustrated in Figure 1 (see Additional Documents, "schema-data-collection.pdf," page 1).

At baseline, participants will complete an on-study form that includes demographics and clinical characteristics as well as questionnaires (see below). We will obtain a baseline body weight measurement. For one week (week 0), participants will wear an actigraph (i.e., activity tracker) and a continuous glucose monitor and complete a food log using the myCircadianClock app.

After the baseline period, they will be randomized 1:1, TRE:control. Those in the time-restricted eating group will be asked to eat all food and beverages in a self-selected 10-hour window during the day. The start time of the window can be chosen based on the participant's schedule and preferences, but it should be the same for the duration of the study. We will not restrict what people eat. Black coffee and unsweetened tea will be allowed before the window, and water and medications are allowable any time. Those in the control group will be asked to not make any changes to their current dietary patterns.

For the duration of the 12-week study, all participants may engage with the myCircadianClock app (see below) as much or as little as they like—with user input the app monitors eating, exercise, sleep patterns, and other measures. Also, the app will deliver weekly health tips and provide reminders about study activities (e.g., "Remember to weigh yourself today!"). To ensure that weight loss does not occur at an unhealthy rate, we will be providing participants with a bathroom scale for weekly measurements. Approximately every two weeks, the participant will receive a call from a study team member to check in; ask about symptoms and gauge use of the myCircadianClock app; ask about eating, sleeping, and exercise patterns; and for those in the TRE group, discuss adherence to the TRE pattern including barriers and how to overcome any barriers (See Engagement Script). During week 6 (midpoint), participants will be asked to complete questionnaires, log their sleep and eating habits using the app, wear the actigraph, and wear a continuous glucose monitor. During the last week of the study, week 12, participants will again be asked to complete questionnaires, log sleep and eating habits using the app, wear the actigraph, and wear a continuous glucose monitor. After completion of the study, participants will be asked to participate in a semi-structured interview during which we will solicit feedback on the study—what they liked about it, what they did not like about it, if they would recommend it to friends, etc. This will last approximately 15-30 minutes and will be audio-recorded with specific permission. Participants will receive \$25 at each time point if they complete at least 3/4 of the baseline, week 6, and week 12 study activities (5+ days of logging food intake, questionnaires, actigraphy, and continuous glucose monitoring) for a total of \$75; we will emphasize the importance of the food logs and questionnaires to answer our primary research questions. After completion of the study, those in both groups will have continued use of the myCircadianClock app.

myCircadianClock application ("app").

The myCircadianClock app is designed to run on both Android and iOS devices that account for more than 90% of all smartphones and uses HIPAA-compliant Amazon Web Server (AWS) for server-side operations. A dedicated team of developers make periodic updates to the app and to the backend server to comply with updates released by Apple, Google, and Amazon. The server side is designed to run multiple independent studies and the app is designed for individual customization. This allows study-specific customization by the investigator and user-specific customizations by participants. For those in the intervention group, participants can set their daily eating periods and receive alerts and reminders specific to their eating window. For example, participants can receive an automated alert 15 or 30 minutes prior to the end of the eating interval to finish their last meal of the day. All subjects can log their food, sleep, and activity via the app. The research team can visualize real-time data from individual participants and will receive a daily summary of data logs. For food entries, the user can annotate the food picture with food name and any other descriptor (portion size, left over etc.). The app will be customized to add push notifications, reminders, and educational materials that are structured to guide the participants throughout the study, enable self-monitoring, and improve compliance. This app is user-friendly and has been used in several circadian rhythm clinical trials. Data collected from the app will include all user inputs (i.e., photos or names of food/beverages, activity/exercise, sleep, and health entries) as well as language, timestamp of entries, and geographic location data from entries (to obtain country and time zone information). Entering food and sleep behaviors will total approximately 5 minutes/day during weeks 0-12.

Food Record:

Participants will be asked to record all foods and beverages consumed during all seven days of Week 0, Week 6, and Week 12 using the myCircadianClock app (the "Food Record"). It will take the participants about 30 seconds per meal to enter the data. The default mode of collecting food data is to take a picture and add a short description (e.g., bagel with cream cheese). The app stores previously entered food, so it is fast and easy to record habitual meals. Participants can also scan a barcode or QR code of a food/beverage to obtain manufacturer's nutritional information. With each entry, the app asks whether the event is current or in the past and, if in the past, what time. The Food Record will be analyzed for total calories, macronutrients, micronutrients, and bioactive compounds using Nutrition Data System for Research (NDSR; Regents of the University of Minnesota, Minneapolis, MN) or a similar program. The Food Record will also be analyzed for eating window (time between first and last calorie) and other aspects of eating patterns.

Questionnaires:

Questionnaires will be administered at baseline (Week 0), Week 6, and Week 12. Questionnaires will be administered via REDCap or on paper and then manually entered into REDCap. There are a total of 9 questionnaires. The On Study form will be completed at baseline only, and the 8 others will be completed at Week 0, Week 6, and Week 12. The battery of questionnaires will include the following:

1. Functional Assessment of Chronic Illness-Fatigue (FACIT-F) questionnaire: The FACIT-F is a 40-item, validated, commonly used measure of fatigue that is comprised of five subscales: physical well-being, social well-being, emotional well-being, functional well-being, and fatigue. It captures symptoms in these categories over the last 7 days.
2. Brief Fatigue Inventory (BFI): The BFI is a 10-item fatigue questionnaire that is also validated and commonly used. It captures fatigue now and the usual and worst in the last 24 h. It also includes 6 single-item questions regarding how fatigue has interfered with general activity, mood, work, etc.
3. Symptom Inventory (SI): The symptom inventory (modified from the MD Anderson Symptom Inventory) includes 19 items that are common in the cancer experience (e.g., pain, distress, lack of appetite, numbness and tingling), as well as 8 items related to how much these symptoms interfere with activities of daily living and quality of life. Many symptoms often correlate with each other including fatigue (i.e., symptom clustering), so it is important to capture the change in many symptoms from baseline to post-intervention.
4. Positive and Negative Affect Schedule (PANAS)-SF: The PANAS-SF is a 20-item measure of mood. It asks the extent to which a person has felt certain emotions (e.g., enthusiastic, proud, irritable) over the last week. There are 5 response choices ranging from 1 (very slightly or not at all) to 5 (extremely). It has been deemed reliable and valid in the non-clinical population and is routinely used in the cancer survivorship population.
5. Brief Pain Inventory-Short Form (BPI-SF): The BPI-SF assesses severity of pain and its impact on functioning. If a person reports feeling pain, it asks what area(s) hurt the most; a pain rating from 0-10 for pain at least, worst, and average in the last 24 hours; pain right now; medications taken for pain; and how the pain has interfered with general activity, mood, walking, work, relations with other people, sleep, and enjoyment of life. The BPI-SF has been validated and has been deemed reliable in the cancer population.
6. Insomnia Sleep Index (ISI): The ISI is a 7-item questionnaire that assesses sleep quality. It assesses difficulties falling asleep, staying asleep, waking up too early, satisfaction with sleep pattern, how noticeable any sleep problem is to others, worry about sleep problems, and interference of sleep problems with daily functioning. It has been deemed reliable and valid in the cancer population.
7. Global Physical Activity Questionnaire (GPAQ): The GPAQ is a 16-item questionnaire designed to estimate an individual's level of physical activity in three domains: work, transportation, and leisure time, as well as time spent in sedentary behavior. It has been deemed valid and reliable to survey and measure changes in physical activity among many diverse populations. It is commonly used in the cancer literature.
8. Multidimensional Assessment of Interceptive Awareness (MAIA)-2: The MAIA is a 37-item questionnaire that evaluates interception, or how much a person is in-tune with sensations from their body. It includes questions such as 'I trust my body sensations' and 'I notice how my body changes when I feel angry.' There is no objective measurement that can be used to validate the MAIA scales and, because interception is a relatively new concept in the field of oncology, it has been only seldom used in the cancer population.

The 8 questionnaires that will be completed at Week 0, Week 6, and Week 12 should take approximately 30-60 min in total to complete.

Circadian rhythm via actigraphy

With a wrist-worn actigraph (e.g., MotionWatch-8) at baseline, week 6, and week 12, we can assess activity in three axes, recorded as "counts." Counts are used to calculate the strength of circadian rhythms as well as deduce active periods and sleep measures (i.e., sleep latency, efficiency, duration; wake after sleep onset; daytime napping). By combining these measures with sleep logs via myCircadianClock, we can infer whether any improvements in fatigue are derived from improved sleep and/or increased daytime activity. These actigraphs also have a light sensor.

The actigraph and glucose monitor (see below) will be mailed to participants approximately one week before they are supposed to wear them. Included in the package will be a prepaid shipping label to return the actigraph, glucose sensor, and sensor reader in the box in which they were sent.

#### Continuous glucose monitoring

At baseline, week 6, and week 12, we will assess interstitial glucose concentrations using a FreeStyle Libre continuous glucose monitor (Abbott Labs). From these data we will extract fasting glucose, average daily glucose, average waking and nocturnal glucose, maximum glucose, and area under the curve. This device is placed on the back of the participant's upper arm for up to two weeks. It is unobtrusive and does not interfere with normal bathing, exercising, or swimming. Data are saved automatically every 15 min. Interstitial glucose reflects blood glucose concentrations, though measures are delayed by 4-15 minutes. The benefit of continuous interstitial glucose monitoring over blood glucose is that it avoids frequent, painful finger pricks or venipunctures.

- These data will be used for research purposes only and not diagnostic purposes. The monitor itself does not have a screen, and it will not be required for the participant to view or interpret their blood glucose data at any time. The researchers will not have access to the data in real-time. The monitors are disposable and will be mailed back to us after they wear them. We will be able to upload the data from the monitor and provide the data to the participant upon request at the end of the study, and the participant will be able to share their results with their provider if they are concerned with their glucose regulation.

-If any individual happens to observe a hyperglycemic event of greater than about 200 mg/dl (11.1 mM) and told us, we will discuss the circumstances surrounding the event with the participant and any symptoms that might have cooccurred, and we will discuss the event with the study doctor. We will decide what course of action to take, including encouraging the participant to talk to their primary care physician. It is very unlikely that time-restricted eating will cause hyperglycemia, so it is unlikely but possible that we will withdraw them from the study if they are in the intervention arm.

-If an individual happens to observe a hypoglycemic event less than about 70 mg/ml (3.9 mM) and told us, we will similarly discuss the circumstances and symptoms surrounding the event and discuss the event with the study doctor, [name]. We will decide on the best course of action, which might include lengthening the eating window or withdrawing the person from the study if they are in the intervention arm.

-Data from the continuous glucose monitors will be compiled and analyzed at the end of the study. Therefore, neither the study coordinators nor the participants need directed training to monitor or interpret glucose levels during the study.

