## Research Related Risks

**If you uploaded a separate research protocol document in the 'Research Protocol' page, cite the applicable section and page numbers from that document in the answer box below.**

1 \* Individually list each research-related risk, using a separate line for each. Next to each risk, delineate the likelihood/seriousness of the risk, and the provisions for minimizing the risk:

a) Weight loss due to the intervention

Some studies have documented weight loss upon adoption of a TRE dietary pattern (10 hours of feeding/14 hours of fasting) despite consuming calories ad libitum. This intervention diet will be ad libitum and participants will be encouraged to satisfy thirst and hunger. However, due to the time-restrictive nature of the TRE diet compared to the typical American eating patterns, there is a chance that patients could enter a calorie deficit and lose weight during the course of the intervention. Minor weight loss will not be considered an adverse event (less than 3% in one week or 5% body weight every two weeks). However, if a patient experiences rapid, unintentional weight loss, the participant will be encouraged to contact the study team, medical monitor, and/or their treating oncology team. The CTCAE, version 5, will be used to report weight loss as an adverse event:

- Weight loss of 5% to less than 10% from baseline with no intervention indicated will be considered a Grade 1 adverse event.

- Weight loss of 10% to less than 20% from baseline and indicated nutritional support will be considered a Grade 2 adverse event.

- Weight loss greater than or equal to 20% from baseline with indicated tube feeding or total parenteral nutrition (TPN) will be considered a Grade 3 adverse event.

Weight loss can cause anxiety in cancer survivors who might think that their cancer is recurring. However, knowing that this dietary intervention often results in weight loss, particularly in people who are overweight, can be reassuring in that weight loss is due to dietary change and not a manifestation of progressive cancer, particularly if there are no other concerning symptoms.

As always, the patient has the right to eat or drink outside of the 10-h window, and to withdraw from the study at any time.

Likelihood: Moderate probability that some weight loss will be experienced, especially in patients with excess body fat; very low probability that a dangerous amount of weight will be lost

Seriousness: Low

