Provisions for minimizing risk: In order to closely monitor weight change, each participant will be provided with a scale to use at home. It is likely that some participants will have personal goals to lose excess body fat—we will explain that this is not a weight loss study. In the event that rapid, unintentional weight loss occurs, the treatment team's recommendations for nutritional interventions due to any weight loss will be followed.

b) Hunger and hunger-related symptoms due to the intervention

Eating within a 10-h window will mean re-adjusting participants' typical eating patterns. Many participants will need to rearrange their meal times—either delay breakfast, eat dinner earlier, and/or forgo after-dinner snacks. If they delay breakfast, they might feel hungry in the few hours leading up to their eating window, especially in the first few days of the study. Similarly, they might crave something before bed if they are in the habit of eating before bed. With hunger can come lack of concentration, fatigue, dizziness, irritability, and other symptoms.

Likelihood: Moderate-high

Severity: Low to moderate

Provisions for minimizing risk: All participants will be encouraged to stay hydrated and to consume a snack outside of the window if symptoms become debilitating.

c) Emotional distress due to the intervention or the outcome measures

There is a chance that participants could become emotionally distressed by the expectation to consume food only in the 10-h window.

Likelihood: Low

Severity: Low

Provisions for minimizing risk: Each participant will be reassured that deviations from the plan are permitted, especially if they are feeling sluggish, dizzy, or sick, or if they are on a short trip/vacation.

d) Breach of confidentiality

There is always a risk of a breach of confidentiality in which sensitive medical information (e.g., medical history, AIDS status) could become known to persons outside the research team.

Likelihood: Very low

Severity: Low to high

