Provisions for minimizing risk: We are excluding participants who have type 1 diabetes, risk for hypoglycemia, or any other contraindications as determined by their provider. People who have type 1 diabetes or are at risk for hypoglycemia tend to know, and know that they should not fast for 14 hours overnight. In the consent form, we describe symptoms that are associated with hypoglycemia. We underlined that we encourage them to eat outside their eating window if they feel sluggish, dizzy, or sick. We will emphasize this while we go over the consent form with them and before they sign it. In the event that hypoglycemia occurs or is expected based on the participant's symptoms, the PI will meet with the participant to discuss the events surrounding the hypoglycemic episode and then meet with [name], the study doctor, to determine the course of action, which might include extending the eating window or having the participant stop the study.

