**2 \* Describe procedures for orderly termination:**  
Upon completion of data collection and return of the actigraph, each participant will be thanked for their participation in the study and compensated for their time.

If a participant withdraws (or is withdrawn) before the end of the study, they will be paid for the time they spent providing data and the study team will not contact the person anymore. A 10-20% withdraw rate is built into the study design and recruitment goal, so there should not be a need to replace participants who withdraw before completing the study.

**3 \* Describe procedures that will be followed when subjects withdraw from the research, including partial withdrawal from procedures with continued data collection:**  
If a participant wishes to withdraw from the study, we will ask if the participant would like to continue participation in some but not all of the research activities. If they would like to participate in only some of the research activities, we will note which ones and the participant will not be formally withdrawn from the study. If they wish to withdraw completely, a written withdrawal request is required and should be sent to the PI (email preferred). The written request for withdrawal will be included in the participant's study record as documentation of the reason for removing a participant from the study. If a participant makes a verbal request and does not provide a written request, the verbal request will be documented by the study team member who receives the request and added to the participant's study record. Data that have been collected thus far will be analyzed.

ID: VIEW4E1B5251F800  
Name: v2\_Withdrawal of Participants

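### Minor: if the team withdraws a TRE participant after a glucose event, remaining fatigue scores are lost; extend the partial-participation offer to cover this case

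*Combined protocol and SAP*

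**What the plan says.** In the combined protocol and SAP, Study Procedures item 1 (Continuous glucose monitoring) covers events that a participant notices and reports. For low glucose, the team discusses the event with the participant and the study doctor and chooses a response, "which might include lengthening the eating window or withdrawing the person from the study if they are in the intervention arm". For high glucose, "it is unlikely but possible that we will withdraw them from the study if they are in the intervention arm". Research Related Risks item 1(e) gives a similar choice for hypoglycemia that has occurred or is suspected from symptoms, "which might include extending the eating window or having the participant stop the study".

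The same section also offers milder responses that keep people enrolled. Of symptoms it says that "we encourage them to eat outside their eating window if they feel sluggish, dizzy, or sick". Under weight loss, "the patient has the right to eat or drink outside of the 10-h window". Under emotional distress, "deviations from the plan are permitted, especially if they are feeling sluggish, dizzy, or sick".

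Withdrawal of Participants item 2 sets out what follows withdrawal: "If a participant withdraws (or is withdrawn) before the end of the study", the person is paid for their time and "the study team will not contact the person anymore". Item 3 lets a participant who asks to leave keep doing some activities without being formally withdrawn. It also says that data already collected are analysed.

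Sample Size and Data Analysis item 2 tests Aim 2 through the group-by-time interaction at 12 weeks. It promises analysis as randomised whatever the adherence, and the note on adherence repeats this.

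**The concern.** Stopping an intervention and stopping follow-up are separate decisions, and an as-randomised analysis needs the second to be rare. The plan names two responses to a glucose event: a longer window, or leaving the study. It has no stated route by which the team stops TRE but goes on collecting questionnaires. If the team chose withdrawal, the no-contact sentence would apply, because it expressly covers people who are withdrawn by others. The partial-participation offer would not apply as worded.

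Week 12 fatigue, the Aim 2 time point, would be at stake. The glucose-monitoring text names this withdrawal only for the TRE arm, so any loss by this route would be one-sided and linked to how well the person tolerated TRE. Losing people who did poorly would make TRE look better than it is.

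**Working it through.** **Setting the sections side by side**

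1. Continuous glucose monitoring and Research Related Risks 1(e) allow withdrawal as one option.
2. Withdrawal of Participants item 2 ends contact after withdrawal, whoever decides it.
3. Item 3 offers partial participation only to a participant who wants to leave.
4. Nothing forbids stopping TRE with continued follow-up, but nothing provides for it after a team decision.

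**Which scores are exposed**

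Monitors are worn for 7 days at weeks 0, 6 and 12. Week 0 precedes randomisation, and week 12 wear falls in the same week as the final questionnaires. The monitor route therefore matters mainly at week 6, where withdrawal would cost the week 12 score. Withdrawal over symptoms before week 6 would cost both remaining scores.

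**The plan's own figure**

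From 30 recruited with 10-20% attrition, 30 x 0.90 = 27 and 30 x 0.80 = 24. This agrees with the stated figure of about 25 evaluable. The target is now 50 enrolled for about 25 evaluable, which is 25/50 = 50%. The plan has no power calculation to reproduce.

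**Shift in the TRE mean**

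The plan gives neither an event rate nor a fatigue shortfall, so both are assumptions here. Let k TRE participants be withdrawn, each with a change in fatigue d points less favourable than the rest, with d from 3 to 8. With 13 others remaining (about 25 evaluable in two arms), the observed TRE mean is too favourable by k x d / (13 + k):

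- k = 0: no shift
- k = 1: 3/14 = 0.21 to 8/14 = 0.57
- k = 2: 6/15 = 0.40 to 16/15 = 1.07
- k = 3, a stress case at 3/16 = 19% of the arm: 9/16 = 0.56 to 24/16 = 1.50

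**Against the noise**

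The earlier two-week single-arm study (Justification, Objective, & Research Design item 3) gives an SD of change of 8.1 for the fatigue subscale. Applying it to a 12-week comparison is also an assumption. With 13 per arm, the standard error of the arm difference is 8.1 x sqrt(2/13) = 3.18. One case gives at most 0.57/3.18 = 0.18 standard errors, and the stress case at most 1.50/3.18 = 0.47.

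**Sensitivity**

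- If week 6 is observed and shows half the shortfall, a mixed model recovers part of the loss. The shift is multiplied by 1 - r x 0.5, where r is the correlation between the week 6 and week 12 changes. Assumed r of 0.3 to 0.7 gives factors of 0.85 to 0.65, so 0.57 falls to between 0.49 and 0.37.
- A harsher assumption is that the others improve by 5.3 points (the earlier study's mean change) and the lost person worsens by 5.3. In a TRE arm of 12 this gives 10.6/12 = 0.88 points for one case.
- Precision hardly changes. With 12 TRE and 13 control, 8.1 x sqrt(1/12 + 1/13) = 3.24. With one TRE participant lost, 8.1 x sqrt(1/11 + 1/13) = 3.32.

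**The case against.** The strongest reply is that the plan already does most of what is asked. The list of responses is open-ended. The eating window can be lengthened without a stated limit, and a window lengthened towards usual eating amounts to stopping TRE while staying enrolled. Eating outside the window is allowed, and non-adherers stay in the analysis. The PI meets the participant before any decision about hypoglycemia, which gives an occasion to offer partial participation.

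A loss also needs several things to happen together. The person must notice an event on a monitor without a screen, or have symptoms, and report it. The team must prefer withdrawal to a longer window. The decision must come before the final questionnaires. The person must also have been willing to go on answering. Insulin users and people at risk of hypoglycemia are excluded. The earlier study had no severe adverse events, and 36 of 39 completed all questionnaires and diaries.

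This is a pilot that estimates preliminary efficacy. Scores collected before withdrawal are used, and the missing-data plan includes multiple imputation and, if data are suspected to be missing not at random, pattern mixture models.

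Nearly all of this stands, and it limits the size of the point. It does not close the gap in wording. When withdrawal is the option chosen, item 2 applies and item 3 does not, and no analysis recovers a score that was never collected.

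**Conclusion.** The gap is real but narrow, and closing it is a cheap improvement. With about 25 evaluable in total and an assumed shortfall of 3 to 8 points, one case would move the TRE mean by about 0.2 to 0.6 points, at most about 0.18 standard errors. The direction would probably favour TRE, but that is not shown.

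Three stronger readings are tempting, and the documents do not support them:

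- A reader might infer that a glucose event leads to withdrawal. The text makes withdrawal one discretionary option, and calls it unlikely after high glucose.
- A reader might infer a threat to the retention goal or to the trial. Planning 50 enrolled for about 25 evaluable already allows for far more ordinary dropout than this route is likely to add.
- A reader might infer that the exit interview for early leavers contradicts the no-contact sentence. It can take place at withdrawal, before contact ends. It collects no fatigue score, so it does not fill the gap either.

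Confidence is medium: the textual gap is clear, but its practical effect rests on assumed counts and shortfalls.

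**What to change.** Leave the clinical decision with the study doctor and change the wording in three places:

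- **Withdrawal of Participants item 3:** extend the partial-participation offer to anyone whose TRE the team stops, and ask them to complete the remaining week 6 and week 12 questionnaires, with wearables optional.
- **Withdrawal of Participants item 2:** apply the no-contact sentence only to people who decline further participation or withdraw consent.
- **Continuous glucose monitoring and Research Related Risks 1(e):** name stopping TRE with continued follow-up as an option separate from leaving the study.

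Record the date and reason for each stop, and analyse these participants in their assigned arm.

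The cost is a few sentences, possibly one line in the consent form, and 30-60 minutes of questionnaires per remaining time point for a few people, perhaps none. The questionnaires can be done remotely. If that burden is too great, the FACIT-F alone is listed at 5-10 minutes. Some people will decline, and the change helps only those not yet withdrawn. The same wording could be carried into the follow-on trial.
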